# 10.2.3 Steering committee

The Steering Committee will be established comprising investigators participating in the trial, i.e. not being Novartis/sponsor representatives from the Clinical Trial Team.

The Steering Committee will ensure transparent management of the study according to the protocol through recommending and approving modifications as circumstances require. The Steering Committee will review protocol amendments as appropriate. Together with the clinical trial team, the Steering Committee will also develop recommendations for publications of study results including authorship rules. The details of the role of the Steering Committee will be defined in the steering committee charter.

# 11 Data collection and database management

# 11.1 Data collection

Designated Investigator staff will enter the data required by the protocol into electronic case report forms (eCRFs). The eCRFs will be built using fully validated secure web-enabled software that conforms to 21 CFR Part 11 requirements, Investigator site staff will not be given access to the EDC system until they have been trained. Automatic validation programs check for data discrepancies in the eCRFs, allow modification and/or verification of the entered data by the Investigator staff.

The Investigator/designee is responsible for assuring that the data (recorded on CRFs) (entered into eCRF) is complete, accurate, and that entry and updates are performed in a timely manner. The Investigator must certify that the data entered are complete and accurate

After final database lock, the Investigator will receive copies of the patient data for archiving at the investigational site.

All data should be recorded, handled and stored in a way that allows its accurate reporting, interpretation, and verification.

# **11.2** Database management and quality control

Novartis personnel (or designated clinical research organization (CRO)) will review the data entered by investigational staff for completeness and accuracy. Electronic data queries stating the nature of the problem and requesting clarification will be created for discrepancies and missing values and sent to the investigational site via the EDC system. Designated Investigator site staff are required to respond promptly to queries and to make any necessary changes to the data.

Concomitant treatments and prior medications entered into the database will be coded using the World Health Organization (WHO) Drug Reference List, which employs the Anatomical Therapeutic Chemical classification system. Medical history/current medical conditions and AEs will be coded using the Medical Dictionary for Regulatory Activities (MedDRA) terminology.

Each occurrence of a code break will be reported to the clinical team and monitor. The code break functionality will remain available until study shut down or upon request of Novartis.

Novartis	Confidential	Page 61
Protocol (Version No. 00)		Protocol No. CAIN457ADE15

Once all the necessary actions have been completed and the database has been declared to be complete and accurate, it will be locked **and the treatment codes will be unblinded** and made available for data analysis/moved to restricted area to be accessed by independent programmer and statistician. Any changes to the database after that time can only be made after written agreement by Novartis development management.

# 11.3 Site monitoring

Before study initiation, at a site initiation visit or at an Investigator's meeting, a Novartis/delegated CRO representative will review the protocol and data capture requirements (i.e. eCRFs) with the Investigators and their staff. During the study, Novartis employs several methods of ensuring protocol and GCP compliance and the quality/integrity of the sites' data. The field monitor will visit the site to check the completeness of patient records, the accuracy of data capture / data entry, the adherence to the protocol and to GCP, the progress of enrollment, and to ensure that study treatment is being stored, dispensed, and accounted for according to specifications. Key study personnel must be available to assist the field monitor during these visits. Continuous remote monitoring of each site's data may be performed by a centralized Novartis/delegated CRO. Additionally, a central analytics organization may analyze data and identify risks and trends for site operational parameters, and provide reports to Novartis clinical teams to assist with trial oversight.

The Investigator must maintain source documents for each patient in the study, consisting of case and visit notes (hospital or clinic medical records) containing demographic and medical information, laboratory data, and the results of any other tests or assessments. All information on CRFs must be traceable to these source documents in the patient's file. The Investigator must also keep the original ICF signed by the patient (a signed copy is given to the patient).

The Investigator must give the monitor access to all relevant source documents to confirm their consistency with the data capture and/or data entry. Novartis monitoring standards require full verification for the presence of informed consent, adherence to the inclusion/exclusion criteria, documentation of SAEs, and of data that will be used for all primary variables. Additional checks of the consistency of the source data with the CRFs are performed according to the study-specific monitoring plan. No information in source documents about the identity of the patients will be disclosed.

# 12 Data analysis and statistical methods

The data will be analyzed by Novartis and/or a designated CRO.

The analyses will be conducted on all patient data after database lock for the study. Any data analysis carried out independently by the Investigator should be submitted to Novartis before publication or presentation.

# 12.1 Analysis sets

The following analysis sets will be used in this study:

**Randomized Analysis Set (RAS):** The RAS is defined as all patients who were randomized. Unless otherwise specified, miss-randomized patients will be excluded from the RAS.

**Full Analysis Set (FAS):** The FAS comprises all patients to whom study treatment/reference treatment has been assigned by randomization. According to the intent to treat principle, patients will be analyzed according to the treatment they have been assigned to during the randomization procedure.

**Safety Set:** The Safety Set includes all patients who received at least one dose of study treatment/reference treatment. Patients will be analyzed according to the study treatment received, where treatment received is defined as the randomized treatment if the patient took at least one dose of that treatment or the first treatment received if the randomized treatment was never received.

# 12.2 Subject demographics and other baseline characteristics

Demographic and other Baseline data including disease characteristics will be listed and summarized descriptively by treatment group and in total for the FAS and Safety Set.

Categorical data will be presented as frequencies and percentages. For continuous data, mean, standard deviation, median, minimum, and maximum will be presented.

Relevant medical histories and current medical conditions at Baseline will be summarized by system organ class and preferred term (PT), and by treatment group.

# 12.3 Treatments

The Safety Set will be used for the analyses below. Categorical data will be summarized as frequencies and percentages. For continuous data, mean, standard deviation, median, minimum, and maximum will be presented.

The duration of exposure to study treatment by treatment group will be summarized by means of descriptive statistics using the Safety Set. In addition, the number of patients with exposure of certain thresholds will be displayed. Compliance will be calculated based on documented study drug administrations and syringe counts and displayed by treatment group and study phase.

Concomitant medications and significant non-drug therapies received prior to and after the start of the study treatment will be listed and summarized according to the anatomical therapeutic chemical (ATC) classification system, by treatment group. Prior treatments are defined as treatments taken and stopped prior to first dose of study treatment. Any treatment given at least once between the day of first dose of randomized study treatment and the last day of study visit will be a concomitant treatment, including those which were started pre-Baseline and continued into the treatment period. Treatments will be presented in alphabetical order, by ATC codes and grouped by anatomical main group. Tables will also show the overall number and percentage of patients receiving at least one treatment of a particular ATC.

# 12.4 Analysis of the primary endpoint

# 12.4.1 Definition of primary endpoint

The primary aim of this study will be to demonstrate the superiority of secukinumab compared to placebo in patients with moderate to severe chronic plaque-type psoriasis and NAFLD with respect to PASI90 response at Week 12.

The primary endpoint variable is the PASI90 response at Week 12.

The analysis of the primary variable will be based on the following estimand:

- Analysis set: FAS
- Variable of interest: PASI 90 response at Week 12
- Intercurrent event: study discontinuation effect between secukinumab versus placebo in patients with moderate to severe chronic plaque-type psoriasis and NAFLD irrespective of adherence to treatment. Patients who discontinue the trial prematurely will be counted as non-responders.
- Summary measure: Odds ratio (OR)

# 12.4.2 Statistical model, hypothesis, and method of analysis

The null hypothesis to be rejected is that the OR of a PASI90 response for patients with secukinumab vs. patients with placebo are  $\geq 1$  after 12 weeks.

Let pj denote the probability of a PASI90 response at 12 weeks for treatment group j, j=0,1 where

- 0 corresponds to placebo
- 1 corresponds to secukinumab 300 mg

The following hypotheses will be tested:

 $H_0: (p_0 / 1-p_0)) / (p_1 / 1-p_1)) \ge 1$  versus  $H_A: (p_0 / 1-p_0)) / (p_1 / 1-p_1)) < 1$ 

The primary analysis will be performed comparing treatments with respect to the primary efficacy variable in a logistic regression model with the factors treatment group and center as factors and PASI score at Baseline (Day 1) as covariates. The OR and its 95% confidence interval (CI) and p-value will be given. The primary analysis will be based on the FAS and will be performed when all patients have completed the Week 12 assessment.

# 12.4.3 Handling of missing values/censoring/discontinuations

For the analysis of the primary endpoint PASI90 response at Week 12, all patients of the FAS will be included. A patient with a missing assessment will be considered as a non-responder. Missing values of secondary endpoints or other outcomes (e.g. quality of life, safety or laboratory measurements) will not be replaced.

# 12.4.4 Sensitivity and supportive analyses

A "while on treatment" estimand will be calculated as a sensitivity analysis. It will be based on the following estimand:

- Analysis set: FAS
- Variable of interest: PASI 90 response at Week 12
- Intercurrent event: study discontinuation effect between secukinumab versus placebo in patients with moderate to severe chronic plaque-type psoriasis and NAFLD. A patient with a missing assessment will be considered as a responder if he/she has met the response criterion already at the time of drop out. Otherwise, he/she will be considered as a non-responder. Summary measure: OR.

# 12.5 Analysis of secondary endpoints

# Serum ALT level at Week 12

The analysis of historic data from non-NAFLD patients suggests that the distribution of ALT values might be highly skewed to the left; however, after a log-transformation the distribution appeared quite symmetric, bell-shaped and could be well approximated by a normal distribution. Therefore, the log-transformed ALT-values will be used for the analysis.

For this secondary objective, this study is meant as a Proof-of-Concept study, i.e. to evaluate if there is any evidence for a beneficial effect on this endpoint and to provide the basis for the planning of further, confirmatory studies; therefore a Bayesian methodology seems adequate for the analyses of possible drug effects on ALT.

A sample from the posterior distribution of the difference between treatments of the log(ALT) levels will be produced using the BAYES-option is SAS PROC GENMOD (with the default, non-informative prior). These posterior samples will be re-transformed (exponentiated) and the percentage of samples < 1, < .9, <.8 and <.7 (corresponding to the posterior probabilities of any reduction resp. reductions of at least 10%, 20% or 30% of ALT levels under secukinumab compared to placebo) will be calculated. The study will suggest to continue the development of secukinumab for hepatic inflammation, if the posterior probability of any effect (significance) is at least 90% and if the posterior probability of a relevant effect (> 20% reduction) is at least 50%.

# DLQI at Week 12

The DLQI measures functional disability of adult patients with dermatological disorders and had been utilized as a relevant clinical measure in a range of dermatology clinical trials. The DLQI is a simple, validated, self-administered 10-item questionnaire. The instrument contains 6 functional scales (i.e. symptoms and feeling, daily activities, leisure, work and school, personal relationships, treatment).

Each question is answered with the following response: "not at all," "a little," "a lot," or "very much". Seven scores will be derived from the DLQI: the total score of each of the six dimensions as well as the total score over all items. The higher the score, the more quality of life is impaired.

For total DLQI as well as for each of its 7 sub-dimensions the percentage change from baseline will be derived. Descriptive summary statistics will be provided for absolute values as well as for the percentage change by visit and treatment group. Additionally, the percentage of patients achieving a DLQI-score of 0 or 1 (DLQI 0/1) will be tabulated.

# 12.5.1 Safety endpoints

For all safety analyses, the Safety Set will be used. All listings and tables will be presented by treatment group.

Safety summaries (tables, figures) will include only data from the on-treatment period with the exception of Baseline data, which will also be summarized where appropriate (e.g. change from Baseline summaries). In addition, a separate summary for deaths including on-treatment and post-treatment deaths will be provided. In particular, summary tables for AEs will

summarize only on-treatment events, with a start date during the on-treatment period (i.e. treatment-emergent AEs as defined below).

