Randomization number	A unique identifier assigned to each randomized patient
Screen failure	A patient who did not meet one or more criteria that were required for participation in the study
Source data/document	Source data refers to the initial record, document, or primary location from where data comes. The data source can be a database, a dataset, a spreadsheet or even hard-coded data, such as paper or eSource
Start of the clinical trial	The start of the clinical trial is defined as the signature of the informed consent by the first patient.
Study treatment	Any single drug or combination of drugs or intervention administered to the patient as part of the required study procedures
Study treatment discontinuation	When the patient permanently stops taking any of the study drug(s) prior to the defined study treatment completion date (if any) for any reason; may or may not also be the point/time of study discontinuation
Patient number	A unique number assigned to each patient upon signing the informed consent. This number is the definitive, unique identifier for the patient and should be used to identify the patient throughout the study for all data collected, sample labels, etc.
Treatment arm/group	A treatment arm/group defines the dose and regimen or the combination, and may consist of 1 or more cohorts.
Variable	A measured value or assessed response that is determined from specific assessments and used in data analysis to evaluate the drug being tested in the study
Withdrawal of study consent (WoC)	Withdrawal of consent from the study occurs only when a patient does not want to participate in the study any longer and does not allow any further collection of personal data

## Amendment 1

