#### Figure 3-1 Study design

# 4 Rationale

# 4.1 Rationale for study design

The randomized, double-blind, parallel-group design of this study is aligned with previous studies performed in the indication of plaque psoriasis and registration secukinumab studies. The double-blind design will be maintained throughout the study to ensure reliable efficacy and safety measures are obtained for both treatment groups in patients with moderate to severe plaque psoriasis and coexisting NAFLD. This study involves 2 treatment periods, which will allow exploration of efficacy and safety effects of secukinumab 300 mg up to Week 12 in a placebo-controlled manner and additionally from Week 12 up to Week 24 (with last dose at Week 20) with active treatment only.

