2.1.1 General definitions

"Secucinumab 300 mg s.c." and "Placebo" will be used as terms for treatment groups in the rest of document.

"Date of first administration of study drug/treatment" was defined as the date of the administration of study drug/treatment documented at the randomization visit.

"Date of last administration of study drug/treatment" was defined as the last available date documenting an administration of study drug/treatment.

"Last contact" was defined as the last available date that was documented for a patient irrespective of place of documentation / dataset where the date was given.

"Treatment Period 1" was defined as the period starting with the baseline visit and ending with the visit at Week 12.

"Treatment Period 2" was defined as the period starting with the visit at Week 12 and ending with the visit at Week 24.

Data from the end-of-treatment 1 visit was moved to the originally planned visit closest to the time point of the performance of the end-of-treament 1 visit for patients who discontinued treatment prematurely (irrespective of the reason for discontinuation).

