2.7 Safety analyses

For all safety analyses, the Safety Set was used. All listings and tables were presented by treatment group.

Safety summaries (tables, figures) included only data from the on-treatment period with the exception of Baseline data, which were summarized where appropriate (e.g. change from Baseline summaries). In particular, summary tables for AEs summarized only on-treatment events, with a start date during the on-treatment period (i.e. treatment-emergent AEs as defined below).

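### Adverse-event and death summaries have no treatment-period split and no defined on-treatment window, so events after the Week 12 switch to secukinumab may be counted under Placebo

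*Protocol*

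**What the plan says.** Protocol 12.5.1 states that the AE tables will "summarize only on-treatment events, with a start date during the on-treatment period (i.e. treatment-emergent AEs as defined below"). SAP 2.7 says the same of the final analysis: "summary tables for AEs summarized only on-treatment events, with a start date during the on-treatment period (i.e. treatment-emergent AEs as defined below"). No definition follows in the visible remainder of either safety section.

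The AE tables are by treatment group, system organ class and preferred term, with a second version adding maximum severity (Protocol 12.5.1, SAP 2.7.1). Deaths are summarised on-treatment and post-treatment together (Protocol 12.5.1, SAP 2.7.2). Neither summary is split by treatment period.

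The group label comes from the Safety Set, where "treatment received is defined as the randomized treatment if the patient took at least one dose of that treatment" (Protocol 12.1, repeated in SAP 2.2). SAP 2.1.1 names two groups only, secukinumab 300 mg and placebo. It also fixes two dosing dates. The first administration "was defined as the date of the administration of study drug/treatment documented at the randomization visit". The last administration "was defined as the last available date documenting an administration of study drug/treatment". The protocol glossary defines study treatment as "Any single drug or combination of drugs or intervention administered to the patient as part of the required study procedures", so both study drugs count.

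Protocol 3 and SAP 1.1 plan secukinumab for placebo-randomised patients at Weeks 12, 13, 14, 15, 16 and 20. SAP 2.1.1 defines Treatment Periods 1 and 2, and Protocol 12.3 has compliance "displayed by treatment group and study phase". No AE, death or exposure summary uses the periods.

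**The concern.** Protocol 4.1 gives a purpose for the two periods: they allow "exploration of efficacy and safety effects of secukinumab 300 mg up to Week 12 in a placebo-controlled manner", followed by a phase on active treatment only. A Placebo column that runs past Week 12 does not deliver that comparison, because it mixes time on placebo with time on secukinumab.

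Protocol 4.5 reports that nasopharyngitis, headache and upper respiratory tract infection were the most common AEs in earlier trials and occurred more often on secukinumab. For events like these, pooling would narrow the difference shown between the columns. For events with equal risk on both treatments, such as the serious AEs that the same section reports at similar low incidences, pooling would not distort the contrast.

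The missing window matters separately. Without an end rule, two programmers could produce different AE tables from the same data. The line between on-treatment and post-treatment deaths is also undefined.

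**Working it through.** The documents state no figure on this point, so there is none to reproduce. The check has a textual part and an arithmetic part.

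**Can the window be inferred from other text?** Protocol 8 requires safety contact during the 4 weeks after the last dose. Protocol 10.1.1 requires AE monitoring for at least 30 days after the last dose. Protocol 10.1.3 has serious AEs reported until 30 days after the last study visit. These are collection rules, they differ, and none is offered as an analysis window. SAP section 4, which lists the changes for the abbreviated analysis, adds neither a window nor a split, and it does not drop the AE tables.

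**Planned exposure in the placebo arm** (SAP 1.1: 30 patients; Protocol 3: switch at Week 12 of 24):

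- Dosing visits: 6 with placebo (baseline, Weeks 1, 2, 3, 4, 8) and 6 with secukinumab (Weeks 12, 13, 14, 15, 16, 20), so 6 of 12.
- Patient-weeks on secukinumab: 30 × 12 = 360 of 30 × 24 = 720, or 50%.

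**Post-switch share of a placebo completer's window, by end rule.** Days are from Protocol Table 8-1: switch Day 85, last dose Day 141, Week 24 visit Day 169. Share = (end day − 84) / end day.

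| Window ends at | Calculation | Share |
|---|---|---|
| The switch | – | 0% |
| Last administration, Day 141 | 57 / 141 | 40% |
| Week 24 visit, Day 169 | 85 / 169 | 50% |
| Last dose + 30 days, Day 171 | 87 / 171 | 51% |

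A rule of last placebo dose + 30 days would still overlap the switch: 57 + 30 = Day 87, so 3 of 87 days (3.4%). The end rule therefore has to name the first Period 2 dose.

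**Early termination.** The documents do not say how many placebo patients reached Week 12. Let f be the fraction of placebo patients with a Period 2 dose and w their mean Period 2 follow-up in weeks. Both are assumed, and all placebo patients are assumed to complete Period 1. The secukinumab share of placebo-arm time is f·w / (12 + f·w).

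| | w = 12 | w = 6 | w = 3 |
|---|---|---|---|
| f = 1 | 50% | 33% | 20% |
| f = 0.5 | 33% | 20% | 11% |
| f = 0.25 | 20% | 11% | 6% |
| f = 0 | 0% | 0% | 0% |

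**Direction of the effect, for illustration only.** The documents give no AE risks by arm. Assume a constant event rate λ on placebo and rλ on secukinumab, with everyone followed for 24 weeks. The Placebo column then shows (12λ + 12rλ) / 24 = λ(1 + r)/2, and the apparent rate ratio is 2r / (1 + r). True ratios of 1.25, 1.5, 2 and 3 would appear as 1.11, 1.20, 1.33 and 1.50. A true ratio of 1 stays at 1.

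**The case against.** The strongest reply is that misattribution is an inference. It needs a window extending past Week 12, and no sentence sets one. The SAP dates define first and last administration but are not linked to the on-treatment period. The Safety Set rule decides which group a patient belongs to, not when that patient's events stop counting. This stands as a limit on certainty. It is also the core of the problem, since the plan leaves the answer open between 0% and about half of the window.

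A by-arm summary over 24 weeks is also not wrong in itself. Protocol Table 6-1 lists both placebo and secukinumab under the control arm, so such a table would describe a planned sequence. But the SAP calls that column Placebo, and no table restricted to Period 1 is planned beside it.

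Protocol 4.4 and 12.7 foresee an analysis of Period 1 data. They name no safety table, 12.7 makes the early analysis optional, and the SAP does not carry it forward.

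The practical effect may be small. The study stopped early for low recruitment, no documented figure shows that any placebo patient crossed over, no safety hypothesis test is planned, and AEs are displayed by patient, so a reader could separate them by date. All of this holds, but by-patient displays do not correct the summary tables.

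Finally, parts of both documents are not visible: Protocol 12.6, possibly a safety row in Table 2-1, and some SAP section numbers. A definition could sit there. This is unlikely, because the AE subsections that should contain it read continuously.

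**Conclusion.** The point holds and should be fixed. It is certain on the visible text that AE and death summaries have no period split and that the promised definition is absent from both documents. It is the natural reading, though not certain, that events after the switch count under Placebo. On that reading, the plan as written gives no placebo-controlled AE comparison to Week 12.

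The size for the study as run is unknown and may be zero. The 50% figure rests on 30 placebo patients and full adherence. With partial crossover, under the assumptions shown, the share ranges from 6% upwards. If no placebo patient received a Period 2 dose, nothing is misattributed, but the reference to a definition below still leads nowhere.

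**What to change.** - Define the on-treatment period and treatment-emergent AE in the SAP, with explicit start and end rules.
- Limit the comparative AE and death tables to Treatment Period 1, counting events that start before the first Period 2 dose.
- Show Period 2 events and exposure separately by sequence (secukinumab–secukinumab and placebo–secukinumab), as a short table or a listing given the small numbers.
- If no placebo patient received a Period 2 dose, state that and keep the single table.

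The Safety Set wording can stay if the tables are period-specific. Because the SAP already describes its safety outputs in the past tense, the same clarification may also be needed in the study report.

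The cost is about one paragraph of SAP text and a few extra tables or listings with small counts, which fits the abbreviated analysis. No new data are needed: injection dates and times (Protocol 6.7.2) and AE start dates (Protocol 10.1.1) are already collected.
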